3.1.4 Exclusion Criteria

None of the following exclusion criteria can be fulfilled for QP ExCELS study participation:

- Chronic atrial fibrillation
- Contraindication to CRT-D therapy
- Currently implanted with an endocardial or epicardial left ventricular lead or had prior attempt to place a left ventricular lead
- Cardiac surgical procedure, such as coronary artery bypass graft or valve surgery that is planned to occur within 6 months after implant or ablation that is planned to occur within 90 days after implant (ablations planned to occur prior to or at implant are not exclusionary)

- Expected to receive a heart transplant or ventricular assist device within 12 months
- Life expectancy less than 12 months
- Participation in any other investigational cardiac clinical investigation during the course of the study
- Presence of another life-threatening, underlying illness separate from their cardiac disorder
- Pregnant or breast-feeding at time of enrollment

At the time of MPP screening for inclusion into the MPP sub-study none of the following exclusion criteria can be fulfilled:

- Development of chronic atrial fibrillation since QP ExCELS enrollment
- Received MPP pacing prior to MPP sub-study enrollment

3.2 Methods

3.2.1 eCRFs

During the course of the clinical investigation all clinical procedures are performed according to clinical routine. All parameters and measurements that are recorded within the clinical investigation are described in this section and are documented on the appropriate electronic Case Report Forms (eCRFs). Information from electronically delivered source data (e.g. programmer interrogations, adverse event documentation) will be uploaded to the appropriate eCRF, then captured and stored in a validated environment until the end of the study. The investigator will be required to use an electronic signature to approve the content of the data reported in the eCRFs.

A QP ExCELS Study Termination eCRF should only be completed for early study termination. A QP ExCELS Study Termination eCRF is not required for subjects who complete the 6 month QP ExCELS visit and who are not enrolled into the MPP sub-study. For subjects enrolled into the MPP sub-study, an MPP sub-study specific termination eCRF is required to record a study exit; however, a QP ExCELS Termination eCRF is not required.

BIOTRONIK, Inc. will audit and monitor the content of the eCRFs as described in Section 9. The required procedures and corresponding time schedule for eCRF completion is described in Section 3.3

All data have to be available for source data verification during monitoring conducted by the sponsor. Subjects have to consent to the use of their medical data prior to enrollment by signing the informed consent form.

3.2.2 Subject Demographics, Comorbidities and Medications

After the informed consent has been obtained, demographic information including year of birth, gender, height and weight should be gathered for all subjects.

Furthermore, details regarding illnesses, ECG diagnostics (if obtained within 6 months prior to enrollment), most recent LVEF, the assessment of the current NYHA class, the device therapy indication, comorbidities and current cardiovascular medication should be collected.

3.2.3 Device Settings

The device programming must be medically reasonable. Recommended device settings for participation in this clinical trial are summarized in Table 4:

Table 4: Recommended Device Settings

Parameter	Recommended device settings
BIOTRONIK Home Monitoring®	ON
Capture control LV lead	ON or ATM
Pacing configuration	BiV
LV MultiPole Pacing	OFF*

*In order to support the CRT responder assessment for enrollment into the MPP sub-study, the MPP feature should not be programmed ON prior to enrollment in the MPP sub-study.

3.2.4 CRT Based Lead Measurements

Documentation of the mean sensing amplitude, the pacing threshold and the impedance is required for the LV channel at beginning of device interrogation at implantation and the required 6 month follow-up post-implant. The pacing threshold can be measured either manually or triggered automatically.

The LV pacing threshold is considered **elevated** if the threshold is greater than 2.5 V at 0.4 ms. The LV lead impedance is considered 'out of range' if a measurement is < 200 Ohms or > 3000 Ohms. The LV sensing threshold is considered 'out of range' if a measurement is lower than 2 mV.

The electronic programmer file with the stored measurements is used for source data verification.

3.2.5 New York Heart Association (NYHA) Classification

During the course of the study, the NYHA classification will be utilized for evaluation of the specific level of cardiac disease. The NYHA will be evaluated at all protocol-defined follow-ups. The following bullets provide the definitions for each class:

- Class I: Subjects with cardiac disease, but without resulting limitation of physical activity. Ordinary physical activity does not cause undue fatigue, palpitation, dyspnea, or anginal pain.

- Class II: Subjects with cardiac disease resulting in slight limitation of physical activity. They are comfortable at rest. Ordinary physical activity results in fatigue, palpitation, dyspnea, or anginal pain.
- Class III: Subjects with cardiac disease resulting in marked limitation of physical activity. They are comfortable at rest. Less than ordinary activity causes fatigue, palpitation, dyspnea, or anginal pain.
- Class IV: Subjects with cardiac disease resulting in inability to carry on any physical activity without discomfort. Symptoms of cardiac insufficiency or of anginal syndrome may be present even at rest. If any physical activity is undertaken, discomfort is increased.

The description for each of the classes was taken from the ACC/AHA Guidelines for Implantation of Cardiac Pacemakers and Antiarrhythmia Devices (Gregoratos et al., 1998).

[figure not shown]
3.2.6 Patient Global Assessment (PGA)

During the course of the MPP sub-study a PGA will be given to assess how the subject's overall status has changed since prior to receiving CRT therapy (markedly better, better, unchanged, worse, markedly worse). It is important to minimize the influence on the respondent by limiting their interaction and verbal exchanges with spouses or other individuals who may affect results while the assessment form is being completed.

3.3 Study Procedures

Figure 8 provides an overview of the clinical study design. Details of subject eligibility requirements are noted in Sections 3.1.3 and 3.1.4. Details of other specific study procedures and collected data are noted in Section 3.2.

Figure 8: Clinical Study Design

Assessments of the lead performance are required at the QP ExCELS implant and 6 months follow-up visits. If circumstances prevent the presence of the subject at the in-office follow-up visit, the reason for the missed follow-up has to be indicated on the eCRF. In addition, interim evaluations related to adverse events, system revisions, or heart failure hospitalizations for inclusion into the MPP sub-study will be performed.

Table 5: Required Visit Windows for MPP Sub-Study

Visit Type	Window	Days post-implant
QP ExCELS 6 month follow-up/ MPP Enrollment*	+ 30 days	137 to 227
3 month MPP follow-up	± 30 days	198 to 228
6 month MPP follow-up	± 30 days	288 to 318

*MPP Enrollment may also occur after 3 months post-implant (90 days post-implant) if the subject has a heart failure hospitalization.

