1. INTRODUCTION

1.1 Study Overview

The QP ExCELS study protocol was designed to support a pre-market study phase and an FDA required post-approval registry phase for BIOTRONIK's Sentus QP lead. In addition, the QP ExCELS protocol supports an FDA required post-approval MultiPole Pacing (MPP) sub-study to demonstrate the MPP feature can effectively convert a percentage of CRT non-responders to responders.

Upon completion of the pre-market analysis and approval of the Sentus QP LV lead (P070008/S079, approved May 4, 2017), enrollment into the QP ExCELS study was continued to fulfill the post-approval study requirements. On September 24th, 2019, BIOTRONIK received FDA approval to transition the QP ExCELS Study protocol to the Sentus QP EP PASSION Post-Approval Study Protocol. The purpose of this clinical study protocol amendment is to support the continuation of the MPP sub-study while the QP ExCELS Post-Approval Study protocol is transitioned to the Sentus QP EP PASSION Post-Approval Study protocol.

Subjects eligible for the study are receiving or have recently received a new (*de novo*) implant or undergoing an upgrade from an existing ICD or pacemaker implant with no prior attempt at LV lead placement. Prior to enrollment, eligible subjects will be identified and will provide written informed consent, which will include consent to participate in the QP ExCELS study and the MPP sub-study. Subjects will be screened for the MPP sub-study at the 6 month in-office follow-up, or between 3 months and 6 months post-implant if the patient has a heart failure hospitalization. Those subjects satisfying the MPP sub-study inclusion and exclusion criteria will continue into the MPP sub-study and be seen for additional follow-up visits at 3 months and 6 months after MPP sub-study enrollment (See Section 3.3 for details). No further study visits will be completed for subjects that do not qualify for the MPP sub-study.

All devices utilized in conjunction with this study are U.S. market approved and prescribed by physicians according to approved indications for use.

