2. STUDY DESIGN

The QP ExCELS Study is a multi-center, prospective, non-randomized clinical investigation that includes a sub-study to satisfy an FDA required post-approval study of the MultiPole Pacing feature (PMA P050023/S107) of the Ilivia HF-T QP family CRT-D system (PMA P050023/S103) or Acticor/Rivacor HF-T QP family CRT-D system (PMA P050023/S125).

Subjects enrolled into the QP ExCELS study are ‘provisionally enrolled’ in the MPP sub-study upon signing the Informed Consent Form. Once the subject meets all of the MPP sub-study inclusion and none of the exclusion criteria at the QP ExCELS 6 month follow-up visit, or if a heart failure hospitalization has occurred, the subject may continue into the MPP sub-study, at which point they are ‘fully enrolled’ (as defined in Table 3). No additional subject follow-up is required once the QP ExCELS 6 month follow-up visit is completed, unless the subject is enrolled into the MPP sub-study.

As part of the MPP sub-study inclusion and exclusion criteria, a CRT responder status will be determined for all QP ExCELS subjects. The CRT Responder Classification at QP ExCELS 6-month follow-up will be evaluated by comparing the subject status at the QP ExCELS Enrollment Visit and classified as documented below:

- “Improved”:
 - No HF hospitalization has occurred, AND
 - NYHA class is improved
- “Unchanged”:
 - No HF hospitalization has occurred, AND
 - NYHA class is unchanged
- “Worsened”:
 - HF hospitalization has occurred, OR
 - NYHA class is worsened

Those subjects determined to have a CRT Responder Classification of “Worsened” or “Unchanged” at the MPP enrollment visit may continue into the MPP sub-study if all other inclusion and exclusion criteria are met. After enrollment into the MPP sub-study, the MPP feature will be programmed ON and an MPP optimization procedure may be performed for all subjects according to the site’s preferred optimization method.

Evaluation at the 3-month MPP follow-up (90 ± 30 days post-MPP enrollment) and 6-month MPP follow-up (180 ± 30 days post-MPP enrollment) will include NYHA classification, Patient Global Assessment (PGA), and HF hospitalization status, in addition to collection of the MPP programming. After completion of the 6-month MPP follow-up, subjects may be programmed to MPP or standard BiV pacing, per

physician discretion. Subjects participating in the MPP sub-study will be exited once the MPP sub-study 6 month visit has been completed.

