2.3 Study Size and Duration

The MPP sub-study will enroll up to 110 subjects at up to 75 sites within the United States who are participating in the QP ExCELS study. Based on the previous sample size analysis for the post-approval QP ExCELS cohort, the sample size for the QP ExCELS study is 1754 and will remain unchanged to support continuation of the MPP sub-study (QP ExCELS protocol version February 1, 2017 provides the justification and sample size analysis).

Subjects that enroll in the MPP sub-study will be followed 12 months post-implant, while subjects that do not continue in the MPP sub-study will be followed for 6 months post-implant.

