BIOTRONIK proposes to allow enrollment of any QP ExCELS subject meeting non-responder criteria (“all-comer non-responders”) at the 6-Month Follow-up into the MPP sub-study as it is not standard of care to perform echocardiograms on CRT subjects to determine if they are responding to standard CRT therapy. As such, we estimate that the proportion of non-responders at 6-months that will be converted to responders at 12-months post-implant will be less than that observed in the St. Jude IDE study. There are three additional studies which have published results for CRT response with MPP measured via CCS or NYHA improvement with mid- to long-term follow-up (6 to 12 months) (Forleo et al., 2016; Pappone et al., 2015; Zanon et al., 2016). However, these studies also did not limit multiple point LV pacing treatment to non-responders, thus the results are not directly applicable to the proposed BIOTRONIK study design.

Assumptions:

- Study Design: Superiority Trial
- Type I error (alpha): 0.025 (one-sided)

- Statistical power: 80%
- Performance Goal: 3%
- Expected: 10%

A total of 90 evaluable subjects would be required to demonstrate superiority to a performance goal of 3%.

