3.3.4 QP ExCELS 6-month Follow-up

Six (6) months (\pm 45 days) after implantation, subjects return to the investigational site for an in-office assessment of their implanted system. To support CRT Responder Assessment at 6-months post-implant, QP ExCELS 6-month follow-ups occurring prior to the visit window or more than 30 days after the visit window will not be allowed.

The following data should be collected:

1. Perform device interrogation:
 - Determine LV lead impedance
 - Determine LV lead R-wave sensing amplitude
 - Determine the LV pacing threshold at 0.4 ms pulse width for the programmed pacing vector
 - Determine LV pacing threshold @ any pulse width (allowing for a minimum 2.5 V safety margin) and document occurrence of phrenic nerve stimulation for additional LV pacing vectors.
2. Obtain NYHA classification and HF hospitalization status to determine CRT Responder Assessment classification

3. Screen subject for MPP sub-study by confirming subject meets all of the MPP sub-study specific inclusion criteria and none of the MPP sub-study specific exclusion criteria (Sections 3.1.3 and 3.1.4). If the subject qualifies for the MPP sub-study, complete MPP sub-study enrollment procedures in Section 3.3.5.
4. Device programming and settings at end of follow-up.
5. Store the electronic procedure data (including final device settings, measurements, episodes) of the BIOTRONIK programmer on an appropriate USB flash drive.
6. Complete the appropriate Follow-Up eCRF.
7. Document any reportable adverse event (e.g. phrenic nerve stimulation, high LV pacing threshold, etc.) using the respective eCRF.

If subject does not qualify for the MPP sub-study, no further follow-up visits are required. A study termination eCRF is not required.

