3.3.5 MPP Sub-Study Enrollment

MPP sub-study enrollment occurs after a subject has been screened and determined to meet all MPP sub-study specific inclusion criteria and none of the exclusion criteria. QP ExCELS subjects with a heart failure hospitalization will be considered to have a CRT Responder Assessment classification of worsened and are eligible for the MPP sub-study. Subjects with a heart failure hospitalization occurring prior to the 6 month post-implant follow-up visit may be enrolled between 3 and 6 months post-implant by completing an interim follow-up eCRF (Section 3.3.8.1) or be enrolled at the QP ExCELS 6 month follow-up visit (Section 3.3.4).

MPP optimization may be performed or not performed per investigator discretion at the time of enrollment into the MPP sub-study. The investigator will determine if MPP optimization will be performed for each subject and which method will be used (e.g. QRS width, electrical delay, echocardiography, etc.). MPP programmed parameters may be adjusted as needed during the follow-up period for MPP sub-study subjects.

After a patient has been screened and determined to be eligible for the MPP sub-study, the following data will be collected:

1. Turn MPP ON and collect MPP programmed settings
2. Document MPP optimization method
3. Obtain Patient Global Assessment
4. Document any reportable Adverse Events
5. Review and complete the appropriate eCRFs

The MPP feature must be programmed ON from MPP enrollment until the subject exits the sub-study. Subjects who have the MPP feature permanently turned OFF prior to completion of the sub-study will be required to report a protocol violation.

3.3.6 3-Month MPP Follow-up

At a 3-month MPP follow-up (90 ± 30 days post-MPP enrollment), subjects return to the investigational site for an in-office assessment of their heart failure status and implanted system.

The following data should be collected:

1. Collect MPP programmed settings
2. Obtain NYHA classification and HF hospitalization status
3. Obtain Patient Global Assessment
4. Collect device initial and final programmed settings
5. Document any reportable Adverse Events
6. Review and complete the appropriate eCRFs

3.3.7 6-Month MPP Follow-up

At the 6-month follow-up (180 ± 30 days post-MPP enrollment), subjects return to the investigational site for an in-office assessment of their heart failure status and implanted system.

1. Collect MPP programmed settings

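### Table 5 fixes the 3- and 6-month MPP visits in days from implant, contradicting the text windows counted from MPP enrollment; for enrollment on days 169–227 no date satisfies both

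*Combined protocol and SAP*

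**What the plan says.** The text counts the MPP visits from MPP enrollment. Section 1.1 promises "additional follow-up visits at 3 months and 6 months after MPP sub-study enrollment (See Section 3.3 for details"). Section 2 gives the windows as 90 ± 30 and 180 ± 30 days after MPP enrollment. Sections 3.3.6 and 3.3.7 repeat them, the first as (90 ± "30 days post-MPP enrollment), subjects return to the investigational site for an in-office assessment of their heart failure status".

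Section 3.3, to which Section 1.1 sends the reader, also contains "Table 5: Required Visit Windows for MPP Sub-Study". Its window column shows ± 30 days for both MPP visits. Its day column is counted from implant and reads 198 to 228 for the 3-month visit and 288 to 318 for the 6-month visit. The enrollment row reads 137 to 227, and the footnote opens an earlier route: "MPP Enrollment may also occur after 3 months post-implant (90 days post-implant) if the subject has a heart failure hospitalization".

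Three other statements bear on the point:

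- Section 2.3: "Subjects that enroll in the MPP sub-study will be followed 12 months post-implant".
- Section 2.3.1.1, on the planning assumption: "the proportion of non-responders at 6-months that will be converted to responders at 12-months post-implant".
- Section 2, on exit: "Subjects participating in the MPP sub-study will be exited once the MPP sub-study 6 month visit has been completed".

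Section 3.3.4 sets the routine enrollment visit at 6 months ± 45 days and adds a late tolerance: "6-month follow-ups occurring prior to the visit window or more than 30 days after the visit window will not be allowed".

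**The concern.** A window measured from enrollment cannot be written as one fixed range from implant when enrollment itself moves over 91 days or more. Table 5 does this, under a title that calls the windows required, and nothing in the document ranks the table against the text.

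The 6-month MPP visit decides the primary endpoint. Subjects leave the sub-study once it is done, so exposure lost to an early visit is not recovered. Section 4.7 says sites receive a schedule showing each subject's visit windows; if that schedule was built from Table 5, the error would carry into practice. Section 2.1.5 also lists compliance with the visit schedule as data of interest, and where the two rules do not overlap, a visit that meets one breaches the other.

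**Working it through.** **Inputs.** Let E be the day of MPP enrollment, counted from implant.

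- Text (Sections 2, 3.3.6, 3.3.7): 3-month visit in [E + 60, E + 120]; 6-month visit in [E + 150, E + 210].
- Table 5 as printed: [198, 228] and [288, 318].
- E runs from 137 to 227 by the routine route (227 − 137 + 1 = 91 days), from day 90 after a heart failure hospitalization, and to 227 + 30 = 257 if the Section 3.3.4 late tolerance is used.

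**Can the printed ranges be reproduced?** The enrollment row can: 182 ± 45 = 137 to 227. Its + 30 days entry is read here as the Section 3.3.4 tolerance and is not counted as an error. The two MPP rows cannot. A ± 30 window spans 60 days, while 228 − 198 = 318 − 288 = 30, so no E gives either range. A ± 15 window gives both only at E = 123 (213 − 90 = 303 − 180 = 123), before the routine window opens. Alternatively, E = 138 gives 198 = E + 60, 228 = E + 90, 288 = E + 150 and 318 = E + 180, that is, windows cut off at the nominal day. Neither reconstruction is stated in the protocol. Row 1 is intact and rows 2 and 3 have equal spans exactly 90 days apart, so damage in reading the table is unlikely.

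**When do the two rules agree?**

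- Table 5 lies wholly inside the text window if E + 60 ≤ 198 and E + 120 ≥ 228, so 108 ≤ E ≤ 138. The 6-month limits give the same range. Only days 137 and 138 are routine days: 2 of 91.
- Some overlap exists if E + 60 ≤ 228 and E + 150 ≤ 318, both giving E ≤ 168. The opposite limits give E ≥ 78, so every enrollment on days 90–168 has some common date.
- No overlap for E = 169 to 227: 227 − 169 + 1 = 59 days, out of 91 routine days or out of 138 days counted from day 90.

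**What each rule means for given enrollment days** (MPP is switched on at enrollment, so days on MPP = visit day − E):

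| E | Text, 3-month | Text, 6-month | Days on MPP at a Table 5 6-month visit (288 − E to 318 − E) |
|---|---|---|---|
| 90 | 150–210 | 240–300 | 198–228 |
| 137 | 197–257 | 287–347 | 151–181 |
| 182 | 242–302 | 332–392 | 106–136 |
| 227 | 287–347 | 377–437 | 61–91 |
| 257 | 317–377 | 407–467 | 31–61 |

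The text rule allows 150–210 days on MPP. For E = 227 the printed 3-month range runs from 198 − 227 = −29 to 228 − 227 = +1 days relative to enrollment.

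**Most generous reading.** Adding ± 30 to the printed ranges gives [168, 258] and [258, 348]. Overlap then needs E + 60 ≤ 258 and E + 150 ≤ 348, so E ≤ 198. Day 182 now overlaps, on days 332–348 for the 6-month visit, but days 199–227 still do not: 29 of 91.

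**Against the 12-month horizon.** The printed 6-month range falls 365 − 318 = 47 to 365 − 288 = 77 days before day 365; even 348 is 17 days short. Under the text rule a day-182 enrollee is centred on 182 + 180 = 362.

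**The case against.** The strongest reply is that the intended rule is plain. The text gives it repeatedly, the Summary speaks of a further 6 months of follow-up, and Table 5's own ± 30 entries agree with it. Only one column is wrong, and for late enrollees that column is visibly unworkable, since the 3-month range starts before enrollment. Section 2.6.2 analyses all available data from fully enrolled subjects and no rule excludes out-of-window visits, so no data would be discarded. Section 4.7 does not say the scheduling tool takes its windows from Table 5.

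Much of this stands. The text rule is very probably the intended one, and where it is applied nothing moves. The harm is conditional on a site or tool following the table.

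Three supporting points also carry limited weight. The day-123 inference assumes symmetric windows, and the day-138 reconstruction fits as well. The 12-month horizon is nominal: the text rule also departs from it, giving days 240–300 for enrollment on day 90 and 377–437 for day 227. And full containment on 2 of 91 days is stricter than a site needs, since any common date satisfies both rules.

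None of this removes the contradiction. The timing of the primary-endpoint visit should not depend on the reader guessing which of two rules was meant.

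**Conclusion.** The concern holds. Table 5 contradicts the text on the timing of both MPP visits and is inconsistent within itself. As printed, no date meets both rules for enrollment on days 169–227 (59 of 91 routine days); on the most generous reading, for days 199–227 (29 of 91). These are calendar days. The distribution of enrollment dates is not given, so they do not translate into a share of subjects.

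If Table 5 were followed, routine enrollees would usually be rated and exited earlier than the text intends, whereas a day-90 enrollee could be rated later. The direction of bias in the responder rate is not established: shorter exposure leaves less time to improve but also less time for a disqualifying hospitalization or death. Sample size, significance levels and analysis population do not change. This is most likely a table error, but it affects the primary-endpoint visit and should be corrected.

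**What to change.** In Table 5, replace the two MPP rows with 60–120 days and 150–210 days after MPP enrollment. State the enrollment row as 182 ± 45 days after implant (137–227), write out the Section 3.3.4 late tolerance to day 257, and keep the footnote on enrollment from day 90 after a heart failure hospitalization. Confirm that any visit-schedule tool given to sites uses the same windows.

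The cost is one table correction and one check of the tool. It adds no visits, subjects or analysis rules.
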